9.6 Procedures for Recording Adverse Events

The patient information sheets will include all possible adverse events relevant to MR scans and ketone supplementation. Potential risks are outlined in section 8.2.4.

All AEs occurring during the study that are observed by the Investigator or reported by the participant, will be recorded on the CRF, whether or not attributed to study investigations.

The following information will be recorded: description, date of onset and end date, severity, assessment of relatedness to trial medication, other suspect drug or device and action taken. Follow-up information should be provided as necessary.

The severity of events will be assessed on the following scale: 1 = mild, 2 = moderate, 3 = severe.

AEs considered related to the study assessments as judged by a medically qualified investigator or the Sponsor will be followed either until resolution or the event is considered stable.

It will be left to the Investigator's clinical judgment to decide whether or not an AE is of sufficient severity to require the participant's removal from the study. A participant may also voluntarily withdraw from the study due to what he or she perceives as an intolerable AE. If either of these occurs, the participant must undergo an end of trial assessment and be given appropriate care under medical supervision until symptoms cease, or the condition becomes stable.

9.7 Reporting Procedures for Serious Adverse Events

In keeping with HRA guidelines, reports of Serious Adverse Events (SAEs) that are related and unexpected will be submitted to the REC using the HRA Non-CTIMP safety report to REC form within 15 days of the chief investigator becoming aware of the event and will be reported to the sponsor within 1 working day of the research team becoming aware of the event. Events will be followed up until the event has resolved or a final outcome has been reached.

10 Description of Statistical Methods

Statistical Analysis: Non-normally distributed data will be transformed to achieve normality prior to analysis, where possible. Bivariate correlations will be performed using Pearson's or Spearman's method, as appropriate. Two-tailed paired *t*-test will be used for: i) Comparisons between rest and stress energetics in patients with and without oral ketone ester supplementation; ii) Comparisons between rest and stress myocardial flow in patients with and without oral ketone ester supplementation; iii) Comparisons between rest and stress LV EF in patients with and without oral ketone ester supplementation.

Power Calculations: Leading on from this previous work, the current proposal aims to advance our understanding of the link between myocardial insulin resistance and rest and haemodynamic stress energetics, perfusion and contractile function in patients with T2D and in patients with heart failure with reduced ejection fraction. Our previous work(40) showed the mean (SD) PCr/ATP ratio with exercise for

Document: Research Protocol		
Short Title: KICK-Energy Version 2.0		
Chief Investigator: [name]	Date 09 Mar 2023	
IRAS Project ID: 308642	Page 23 of 32	

T2D patients to be 1.54 (0.26), compared to 2.07 (0.35) for healthy controls, a difference of 0.53. While we do not have pilot data for the effect of ketone supplementation on myocardial energetics in T2D patients or in HF patients, we propose that increasing the PCr/ATP ratio for T2D patients by one third of this difference (0.18) would constitute a biologically significant effect. Assuming that dobutamine stress energetics with ketone supplementation is associated with an increase from the baseline dobutamine stress energetics of this size, and assuming the SD to be 0.26 as in our previous studies, a group size of 25 would have 90% power, based on a one-way analysis of variance at a 5% significance level. Allowing for a conservative loss to follow-up, we shall recruit 30 T2D patients and 30 patients with heart failure with reduced ejection fraction. 30 healthy controls will be recruited to compare the impact of oral ketone supplementation in patients with diabetes or in patients with heart failure to healthy controls.

10.1 The Level of Statistical Significance

Statistical significance will be considered at P value of 5% significance and a power of 90%.

10.2 Procedure for Accounting for Missing, Unused, and Spurious Data.

Spurious and missing data will lead to data from that participant being excluded from the study.

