8.4 Discontinuation/Withdrawal of Participants

Each participant has the right to withdraw from the trial at any time. In addition, the Investigator may discontinue a participant from the trial at any time if the Investigator considers it necessary for any reason including:

- Pregnancy
- Ineligibility (either arising during the trial or retrospectively having been overlooked at screening)
- Significant protocol deviation
- An adverse event to gadolinium contrast or dobutamine injection during the baseline visit
- Withdrawal of Consent

Document: Research Protocol	
Short Title: KICK-Energy	Version 2.0
Chief Investigator: [name]	Date 09 Mar 2023
IRAS Project ID: 308642	Page 19 of 32

Where patients wish to withdraw from the study, clarification of the extent of withdrawal will be sought and documented in the CRF. Patients who withdraw from the study will be replaced.

If the participant is withdrawn due to an adverse event, the Investigator will arrange for follow-up visits or telephone calls until the adverse event has resolved or stabilised.

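### Section 10.2 removes a participant from the whole study for any missing or spurious item, so valid paired PCr/ATP data are lost to faults in other measurements

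*Protocol*

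**What the plan says.** Section 10.2 of the protocol states: "Spurious and missing data will lead to data from that participant being excluded from the study". The unit removed is the participant and the scope is the study. No other section confines the exclusion to the endpoint concerned, keeps partial data or says what makes a value spurious.

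Three other places bear on it:

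- Section 8.4 (withdrawal): "Patients who withdraw from the study will be replaced". No replacement is stated for participants excluded under 10.2.
- Section 10, Power Calculations: "a group size of 25 would have 90% power, based on a one-way analysis of variance at a 5% significance level", followed by "Allowing for a conservative loss to follow-up, we shall recruit 30 T2D patients and 30 patients with heart failure with reduced ejection fraction". The margin is therefore 5 in 30 per group. No expected loss rate is given.
- Section 10, Statistical Analysis: "Two-tailed paired *t*-test will be used for" the comparisons of energetics, myocardial flow and LVEF.

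Section 8.3 plans blinded image analysis, with the key withheld until analyses are complete and the database is locked.

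**The concern.** A paired test on PCr/ATP needs only the PCr/ATP values from the two visits. Section 10.2 makes a participant's place in that test depend on every other measurement as well.

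The acquisition order in Section 8.2.2 shows how this can happen. Rest and stress spectroscopy are done around the first dobutamine infusion. Stress perfusion follows under a second infusion with contrast, and rest perfusion comes after a washout. If something fails late in the session, the PCr/ATP data already exist, yet the rule discards them. A missing blood result (Section 8.2.1) has the same effect.

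Two things are at stake: precision on the primary endpoint, given up for no gain, and a primary analysis confined to participants with complete, accepted data on everything.

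**Working it through.** **The plan's own figure.** Inputs from Section 10: effect 0.18 (one third of 0.53), SD 0.26, two-sided 5%, 90% power. If 0.26 is taken as the SD of the within-person change, the standardised effect is 0.18/0.26 = 0.692. The paired t-test (noncentral t) then needs 23.9, so 24; power at 25 is 91.3%. With the unrounded effect 0.53/3 = 0.177, power at 25 is 90.3%. So 25 reproduces as a paired calculation. It does not reproduce as a one-way ANOVA of two independent groups (67% at 25). That is a separate matter; the paired figures are used below.

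**Power as the group shrinks (effect 0.18, SD of change 0.26).**

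| Analysed | 25 | 24 | 23 | 22 | 21 | 20 |
|---|---|---|---|---|---|---|
| Power | 91.3% | 90.1% | 88.7% | 87.2% | 85.5% | 83.6% |

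**How many the rule removes.** The protocol gives no failure rate, so the rate per item, *p*, is an assumption. Take 12 imaging items: rest and stress (2) × PCr/ATP, LVEF, perfusion (3) × visits (2). Strain, late enhancement and blood values are left out, although 10.2 covers them too. Two extremes bracket the correlation:

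- Independent failures, all 12 items: loss = 1 − (1 − *p*)^12.
- Failures fully shared within a visit: loss = 1 − (1 − *p*)^2, whichever items count.
- Only the four PCr/ATP measurements count, independent failures: loss = 1 − (1 − *p*)^4.

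Expected number left of 30 in brackets:

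| *p* | Fully shared within visit (either rule) | Whole-participant rule, independent | PCr/ATP only, independent |
|---|---|---|---|
| 2% | 4.0% (28.8) | 21.5% (23.5) | 7.8% (27.7) |
| 3% | 5.9% (28.2) | 30.6% (20.8) | 11.5% (26.6) |
| 5% | 9.8% (27.1) | 46.0% (16.2) | 18.5% (24.4) |

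The avoidable loss is the gap between the two rules. At 2% it runs from zero (fully shared) to 21.5 − 7.8 = 13.7 percentage points (independent), or about 4 of 30 participants. In the independent case the standard error of the primary change is larger by a factor of √(27.7/23.5) = 1.09.

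**When 25 is breached.** This takes a sixth exclusion. With independent failures at 2%, the probability that a group of 30 ends below 25 is 0.65 under the whole-participant rule and 0.03 if only PCr/ATP counts. For a participant-level loss of 5%, just above the fully shared 4.0%, it is 0.003. The average loss reaches 5 in 30 at *p* = 1 − (25/30)^(1/12) = 1.5% with independent failures, and at *p* = 1 − (25/30)^(1/2) = 8.7% with fully shared failures.

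**The case against.** Much of the case on the other side is sound.

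- **Correlation.** Items in one session share causes: a missed visit or an aborted scan removes several at once. The independent column is an upper extreme. At the other extreme the rule costs nothing extra. This stands, and is why only a range is given. Full sharing is also unrealistic, because perfusion follows spectroscopy and can fail alone.
- **Power.** The figure of 25 is not a cliff; losing one or two more participants costs little.
- **The paired test needs both visits anyway.** Anyone without Visit 2 drops out of it whatever 10.2 says. The rule's own harm is limited to participants with usable pairs. For the same reason a mixed model is not required: with two time points and no concurrent untreated arm, a participant with Visit 1 only adds little to the estimated change.
- **Blinding.** Section 8.3 already limits exclusion driven by imaging values. However, 10.2 does not tie the judgement of spurious to the blinded reader, and it also covers non-imaging data.

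A reader might make three stronger inferences that the protocol does not support. First, that replacing withdrawals helps to push a group below 25: replacement protects the head count, and only exclusions under 10.2 can cause that shortfall. Second, that replacing withdrawals contradicts recruiting extra for loss to follow-up: these can be different losses, since a participant who does not return, or whose spectrum fails, need not have withdrawn. Third, that the result is biased in a known direction: replacement can add to the selection of completers, but nothing in the protocol allows the size or sign of a bias to be computed.

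**Conclusion.** The concern holds as a defect in a stated rule, not as a detail left to an analysis plan. Section 10.2, applied literally, discards valid primary data because of faults elsewhere and narrows the primary analysis to fully complete participants. At an assumed 2% failure per item, the loss is about 4% to 22% of participants, against about 4% to 8% if only PCr/ATP counts. The true position within these ranges depends on failure rates and correlations that the protocol does not state.

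The effect on power is modest under the plan's assumptions (90.1% at 24, 85.5% at 21). Those figures require 0.26 to be the SD of change, which implies a within-person correlation of about 0.5 if the SD at each visit is 0.26; at a correlation of 0.25, power at 25 would already be 77%. The loss of usable primary data is reason enough to change the rule, whether or not any group falls below 25.

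**What to change.** Reword Section 10.2 so that:

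1. each endpoint is analysed on all participants with paired data for that endpoint;
2. a spectrum, image or laboratory value is excluded only from the endpoint it affects, on a quality criterion fixed in advance and, for imaging, applied under the blinding already planned in Section 8.3, before the key is opened;
3. all exclusions, withdrawals and replacements are reported by reason and by group.

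Section 8.4 can keep replacement, provided that replaced participants remain visible in the report.

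The cost is a wording amendment and some extra reporting. The number analysed may differ between endpoints, so each result must show its own denominator. The change should be made before the outcome data are seen, because a definition of spurious written afterwards would carry little weight.

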10.3 Procedures for Reporting any Deviation(s) from the Original Statistical Plan

Any deviation(s) from the original statistical plan will be described and justified in the final report, as appropriate.

10.4 Local Steering Committee

A local study steering committee will be set up ([name], [name], [name], [name]) responsible for monitoring of screening, recruitment, auditing consent procedures, data collection, study end-point validation. This committee will meet biannually and assess progress against intermediate bench marks, milestones, and time-based deliverables including:

- 1. Recruitment to date.
- 2. Multiparametric MR analysis.
- 3. Data auditing.
- 4. Dissemination of the findings to academic audiences.
- 5. Dissemination of research to the diabetes community.

11 DATA MANAGEMENT

Document: Research Protocol		
Short Title: KICK-Energy Version 2.0		
Chief Investigator: [name]	Date 09 Mar 2023	
IRAS Project ID: 308642	Page 24 of 32	

All personal data is stored on the NHS server. Anonymised results will be password protected and stored on the University of Leeds server. There will be a master cipher sheet, which will be the only place where participants will be linked to their study number. This will be encrypted and password protected and stored on the NHS server. A separate study spread sheet will contain the anonymised results of the analysis of all study investigations. All data will be anonymised.

Data will be entered into a locally developed electronic database stored on the University of Leeds server. All imaging data, blood results and urine results will be entered into this database. All data will be anonymised on the electronic database.

11.1 Types of data

Clinical measurements such as the following will be collected: demographics, medical history, relevant concomitant medications, 12-lead ECG, clinical laboratory tests, MR study results for patients with diabetes and heart failure and healthy volunteers as described previously for those that participate. These data will be spread across all visits. Safety reporting will be collected as per UK legislation requirements. Other data such as administrative data regarding attendance of visits and patient status in regards to withdrawal will also be collected.

11.2 Methodologies for data collection / generation

Once data is collected, it will be entered into the study specific CRF by site staff in accordance with the protocol requirements. Data will be held for 15 years.

11.3 Formal information/data security standards

Data will be secured in line with Data Protection Act 2018.

11.4 Participant Confidentiality

The study staff will ensure that the participants' anonymity is maintained. The participants will be identified only by a participant ID number on all trial documents and any electronic database, with the exception of the CRF, where participant initials may be added. All documents will be stored securely and only accessible by trial staff and authorised personnel. The study will comply with the Data Protection Act 2018, which requires data to be anonymised as soon as it is practical to do so.

12 SERIOUS BREACHES

Document: Research Protocol		
Short Title: KICK-Energy Version 2.0		
Date 09 Mar 2023		
Page 25 of 32		

A serious breach is defined as "A breach of GCP or the study protocol which is likely to affect to a significant degree: (a) the safety or physical or mental integrity of the subjects of the study; or (b) the scientific value of the study".

In the event that a serious breach is suspected the Sponsor must be contacted within 1 working day. In collaboration with the Chief Investigator, the serious breach will be reviewed by the Sponsor and, if appropriate, the Sponsor will report it to the REC, and the NHS host organisation within seven calendar days.

13 ETHICAL AND REGULATORY CONSIDERATIONS

13.1 Declaration of Helsinki

The Investigator will ensure that this study is conducted in full conformity with the current revision of the Declaration of Helsinki (last amended October 2000, with additional footnotes added 2002 and 2004).

13.2 Guidelines for Good Clinical Practice

The Investigator will ensure that this study is conducted in full conformity with relevant regulations and with the ICH Guidelines for Good Clinical Practice (CPMP/ICH/135/95) July 1996.

13.3 Approvals

Once Sponsor authorisation has been confirmed, the protocol, informed consent form, participant information sheet will be submitted to an appropriate Research Ethics Committee (REC), Health Research Authority (HRA) and host institution(s) for written approval.

Once Sponsor authorisation has been confirmed, the Investigator will submit and, where necessary, obtain approval from the above parties for all substantial amendments to the original approved documents.

13.4 Reporting

The CI shall submit once a year throughout the clinical study, or on request, an Annual Progress Report to the REC, host organisation and Sponsor. In addition, an End of Trial notification and final report will be submitted to the REC, host organisation and Sponsor.

13.5 Expenses and Benefits

Reasonable travel expenses for any visits additional to normal care will be reimbursed on production of receipts, or a mileage allowance provided as appropriate.

We have found in previous studies that provision of transport and light refreshment enhances recruitment and patient experience. This is particularly important given the need for repeat imaging in this study. We will reimburse travel costs incurred by participants when attending for a MR scans.

Document: Research Protocol		
Short Title: KICK-Energy	Version 2.0	
Chief Investigator: [name]	Date 09 Mar 2023	
IRAS Project ID: 308642	Page 26 of 32	

13.6 Other Ethical Considerations

For the participants, this study would require their time and would not directly provide any benefit to the participants themselves. Participants will be reimbursed for reasonable study expenses for travel to and from study visits on production of a receipt. There will not be any payments for participating in this study. Light refreshments will be provided following all of the visits.

14 FINANCE AND INSURANCE

14.1 Funding

Funding for this study awarded by Wellcome Trust.

14.2 Insurance

The University, when acting as Sponsor, has insurance cover in force, which meets claims against it and where those claims arise from the Universities own negligence in its role and activities relating to the study (and which is subject to the terms, conditions and exceptions of the relevant policy). Clinical negligence indemnification will rest with the participating NHS Trust under standard NHS arrangements.

15 PUBLICATION POLICY

The Investigators will be involved in reviewing drafts of the manuscripts, abstracts, press releases and any other publications arising from the study. Authorship will be determined in accordance with the ICMJE guidelines and other contributors will be acknowledged. Anonymized images of the heart and blood vessels may be used in research publications. Copies of any resultant research publications will be sent to participants on request.

Document: Research Protocol		
Short Title: KICK-Energy Version 2.0		
Chief Investigator: [name]	Date 09 Mar 2023	
IRAS Project ID: 308642	Page 27 of 32	

Appendix C: Amendment History

Amendment No.	Protocol Version No.	Date is	ssued	Author(s) changes) of	Details of	f Changes	made		
1	2.0	09	Mar	[name]	Addition	of U&E,	HbA1c,	lipid	and
		2023		and [name]		insulin testing.				

Document: Research Protocol				
Short Title: KICK-Energy	Version 2.0			
Chief Investigator: [name]	Date 09 Mar 2023			
IRAS Project ID: 308642	Page 32 of 32
